8.3.3 Misuse, Medication Error, and Overdose

Study drug misuse, medication error, or overdose should be reported in the same format and within the same timelines as an SAE, even if they may not result in an adverse outcome. In the event of overdose, the subject should be observed closely for signs of toxicity. Appropriate supportive treatment should be provided if clinically indicated.

Overdose is defined as: $\geq 10\%$ above the intended AFM24 planned dose is given or a dose interval <4 days between 2 consecutive doses. If the pharmacy discovers that an overdose has or may have been administered, they should contact the Investigator and Sponsor (or their delegate) immediately.

Medication error is defined as: An unintended failure in the drug treatment process that leads to, or has the potential to lead to, harm to the subject.

Misuse is defined as: Situations where an investigational medicinal product is intentionally and inappropriately used not in accordance with the terms of the current protocol.

8.3.4 Investigational Product Complaints

Pharmaceutical technical complaints associated with the investigational product must be reported to the Sponsor immediately, following the guidance specified in the Pharmacy Manual. The same reporting timelines as for SAEs will apply.

8.4 Follow-Up Information on an SAE

Collection of complete information concerning SAEs is extremely important. Thus, follow-up information that becomes available as the SAE evolves, as well as supporting documentation (eg, hospital discharge summaries and autopsy reports), should be collected subsequently if not available at the time of the initial report and immediately sent using the same procedure as the initial SAE report. The Sponsor (or their delegate) will also review SAE reports for missing information and send queries to the site for resolution as appropriate.

Appropriate diagnostic tests should be performed and therapeutic measures, if indicated, should be instituted. Appropriate consultation and follow-up evaluations should be carried out by the Investigator (or designee). An SAE is followed until it is considered resolved, returns to baseline, is chronically ongoing, stabilized or is otherwise explained by the Investigator. Reporting of Serious Adverse Events to Regulatory Authorities

In accordance with the US Code of Federal Regulations (CFR), Title 21 CFR Part 312.32, the EU Clinical Trial Regulation 536/2014 (EU-CTR), and the ICH Guidelines for Clinical Safety Data Management Definitions and Standards for Expedited Reporting, the Sponsor must submit written documentation in the form of an Investigational New Drug Application (IND) safety report or suspected unexpected serious adverse reaction (SUSAR) reports, respectively. The Sponsor should submit to the regulatory authority all safety updates and periodic reports, as required by applicable regulatory requirements. IND safety reports/SUSARs are required to be reported within 7 calendar days for life-threatening events and those resulting in death or 15 calendar days for all others. These timeframes begin with the first notification of the IND safety reports/SUSARs to the Sponsor or their delegate from the Investigator.

The Sponsor (or their delegate) will determine whether expedited reporting is necessary for SAEs depending on the assessment of seriousness, expectedness, and relationship. In case of

disagreement between the Investigator and the Sponsor regarding causal relationship, the more conservative assessment will determine the reportability of the case.

The Investigator must ensure they are aware and comply with any additional local reporting requirements. For all SAEs regardless of expectedness and relationship, the Sponsor (or their delegate) will assign a case number to be used in all future correspondence regarding the event and can provide a MedWatch or Council for International Organizations of Medical Sciences form describing the event, for the Investigators to report to their IRB/IEC, or other committee. Other SAEs (eg, expected or unrelated SAEs) should be reported per the relevant institution's procedures.

Where required, submission of safety updates by the Investigator to Competent Authorities should be handled according to local regulations. Otherwise, periodic safety reports to the regulatory agencies will be handled by the Sponsor (or their delegate). These safety updates will also include SAEs that do not require expedited reporting to the authorities.

Periodically (at least annually), the IB will be updated to include new and relevant safety information. Until such time that an AE becomes identified in the IB (see Summary of Data and Guidance for the Investigator), it should be considered unexpected.

9.0 STATISTICS

9.1 Analysis Sets

The **safety set** will consist of all subjects who received at least 1 dose of AFM24. The safety set will be the primary population for all safety-related endpoints except determination of the dose-DLT relationship, and for all efficacy related endpoints.

The **DDS** will consist of all subjects in the safety set who have either (a) experienced a DLT at any time during Cycle 1, or (b) met the minimum treatment and safety evaluation requirements without experiencing DLT within Cycle 1 (DLT evaluation period).

At least 2 subjects will be treated in each of the first 2 dose cohorts of AFM24. For all other dose cohorts, at least 3 subjects per cohort will be treated. The DDS will be used for determination of the MTD. The minimum treatment and safety evaluation requirements will have been met if the subject received $\geq 80\%$ of their assigned AFM24 dose in Cycle 1 and completed the 28-day DLT observation period or have had a DLT within the first cycle of treatment to be considered evaluable for DLT. For the first 2 dose cohorts, at least 2 subjects are required to be evaluable for DLT for dose escalation to occur. For subsequent cohorts, at least 3 subjects are required to be evaluable for dose escalation to occur.

The DDS will be used in the BLRM to estimate the dose-DLT relationship.

The **PK set** consists of all subjects who have received at least 1 adequately documented dose of study drug and have at least 1 adequately documented post-dose PK measurement.

Subjects who were screened and have signed the informed consent but did not receive any treatment will be listed including reason for screening failure and any SAE that is related to study procedure. These subjects will not be part of any summary table except for summarizing disposition.

9.2 Missing Data/Discontinuation

Due to the dose escalation design of Phase 1 and the exploratory design of Phase 2a of the study, no imputation of missing values will be done for any analysis (except the imputation for missing partial dates of AEs, response assessments and concomitant medications). Reasons for discontinuation from the study and the study drug will be listed and summarized.

Currently, no drop out during the treatment period is foreseen. However, in the first 2 cohorts of Phase 1 (dose escalation), subjects will be replaced (ie, additional subjects will be added to the cohort) if <2 subjects are evaluable for DLT assessment. In the subsequent cohorts subjects will be replaced if <3 subjects are evaluable for DLT assessment. In the dose expansion phase (Phase 2a), all patients in the **safety set** will not be replaced, independent of the availability of their post-baseline disease assessments.

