7.3 HANDLING OF MISSING DATA

The following approach will be used to impute missing start date of Adverse Events and Concomitant Medications:

- If only day is missing and the month and the year match the date of the first study drug injection, then impute the first date of the study drug injection
- If only day is missing and the month and the year do not match the date of the first study drug injection, then impute the first day of the month
- If the day and the month are missing and the year matches the date of the first study drug injection, then impute the first date of the study drug injection
- If the day and the month are missing and the year does not match the date of the first study drug injection, then impute 01 January of the year

Details of imputation of missing severity and causality for Adverse Events are given in Section 7.8.2. No other imputation for the missing data will be done.

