7.8.2 ADVERSE EVENTS

AEs will be summarized with patient counts, percentages and event counts by MedDRA System Organ Classes (SOCs) and Preferred Terms (PTs). Following categories of AEs will be summarized: AEs, related AEs, SAEs and related SAEs, AEs with NCI CTCAE Grades ≥ 3 , AEs leading to premature discontinuation and interruptions or discontinuation of study drug and TEAEs on day of dosing (up to 24h after the dose) and on the first day after the dose. An event will be considered study drug related if it has 'possible', 'probable' or 'definitely' in relationship to study drug CRF field. TEAEs presented by SOC and PT will also be summarized by severity grades. For all TEAEs' summaries a number of patients with the event will be presented together with the total number of TEAEs.

A worst-case approach will be followed in the event of missing severity or causality data. If the severity is missing, severity grade "4" will be imputed. If causality data is missing, 'Related to study medication' will be imputed.

Listings of AE data (separate for each AE category listed above) will be created.

Summaries of all deaths reported and deaths within 28 days after the last dose of study drug along with causes of death will be created. Listing of the death data will be created.

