9. DEVIATIONS FROM ANALYSIS AS DESCRIBED IN THE PROTOCOL

Apart from the above mentioned change, the planned analyses as described in this SAP do not deviate from the description in the protocol of the analyses to be performed.

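### Protocol 9.2 limits imputation to partial dates, but the SAP imputes missing AE grade and causality and has no rule for partial response-assessment dates

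*Protocol*

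**What the plan says.** **Protocol 9.2** sets a general bar with a short list of exceptions: "no imputation of missing values will be done for any analysis (except the imputation for missing partial dates of AEs, response assessments". Concomitant medications complete the list. Every exception is a partial date. AE severity and causality are not on it.

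**SAP 7.3** opens with its date rules: "The following approach will be used to impute missing start date of Adverse Events and Concomitant Medications". Response assessments are not mentioned. It then points elsewhere for two further items, "Details of imputation of missing severity and causality for Adverse Events are given in Section 7.8.2", and closes with "No other imputation for the missing data will be done".

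**SAP 7.8.2** gives those two rules: "A worst-case approach will be followed in the event of missing severity or causality data". A blank severity becomes Grade 4. For causality, "If causality data is missing, 'Related to study medication' will be imputed".

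**SAP 9** says: "Apart from the above mentioned change, the planned analyses as described in this SAP do not deviate from the description in the protocol". The change it refers to is not identified there, and the section lists no difference in missing-data handling.

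**The concern.** A programmer cannot follow both documents. A blank grade or causality stays missing under the protocol and is filled in under the SAP. A partial response-assessment date may be imputed under the protocol, which gives no method, and may not be under the SAP.

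Two groups of output depend on which text is followed:

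- **Safety:** the Grade 3-or-higher, severity-grade, related-AE and related-SAE tables. Some dose cohorts are very small, so one event can change a reported rate visibly.
- **Efficacy:** PFS and DOR, which SAP 7.7.3 computes from progression, response and scan dates, and the 4-week and 7-week confirmation intervals in SAP 7.7.1. The 4-week interval feeds confirmed response, which is the Phase 2a primary endpoint.

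The severity rule also does not do what its label says. Protocol 8.1.5 has a Grade 5 for fatal events, so Grade 4 is not the worst case.

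**Working it through.** The plan gives no figure to reproduce here. The check is a comparison of texts, followed by simple arithmetic on the size of one affected record.

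**Step 1: the rules side by side**

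| Missing item | Protocol 9.2 | SAP 7.3 / 7.8.2 |
|---|---|---|
| Partial AE date | imputation allowed | start date imputed |
| Partial concomitant-medication date | imputation allowed | start date imputed |
| Partial response-assessment date | imputation allowed, no method given | excluded by the closing sentence of 7.3 |
| AE severity | not allowed | set to Grade 4 |
| AE causality | not allowed | set to related |

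The last three rows conflict. Because SAP 7.3 cross-refers to 7.8.2, the severity and causality rules are deliberate.

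**Step 2: the label of the severity rule**

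The scale in Protocol 8.1.5 runs from 1 to 5, with 5 fatal. Under SAP 7.8.2 a fatal AE with a blank grade is entered as Grade 4. It still counts correctly in the Grade 3-or-higher table. It is wrong in the severity-grade table, which would then disagree with the separate death summary in the same section. At the other end, a mild ungraded AE is entered as life-threatening.

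**Step 3: size for the AE tables**

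If a subject has no other qualifying AE, one imputed event moves the subject-level rate by 100/n percentage points.

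| Group | n | Shift |
|---|---|---|
| Dose Cohorts 1 and 2, minimum (Protocol 3.4) | 2 | 100/2 = 50 |
| Dose Cohort 3 onward, minimum (Protocol 3.4) | 3 | 100/3 = 33.3 |
| Extended dose cohort (Protocol 3.4) | 6 | 100/6 = 16.7 |
| Expansion Cohort B at its early stop (Protocol 3.8) | 8 | 100/8 = 12.5 |
| Phase 1, upper estimate (Protocol 3.10) | 41 | 100/41 = 2.4 |

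If the subject already has a qualifying AE, the shift in the subject rate is zero.

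**Step 4: size for the date-based outputs**

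- A date with only the day missing can be wrong by up to 30 days in a 31-day month. On the SAP's scale that is 30/30.4375 = 0.99 month of PFS or DOR.
- Confirmation intervals are 4 weeks = 28 days and, for stable disease, 7 weeks = 49 days. Early scans are scheduled 8 weeks = 56 days apart. If the second scan falls on the 31st and its day is lost, the gap could be read as anything from 56 − 30 = 26 days to 56 days. That range straddles both thresholds, so confirmation cannot be determined without a rule.

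Neither document says how such a subject's time or confirmation status would be derived.

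**The case against.** The strongest defence has four parts.

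- **The rule is conservative and pre-specified.** Counting unknowns as severe and related is a common safety convention. This stands as a reason to keep the rule. It does not remove the conflict with Protocol 9.2, and it does not cover fatal events.
- **Blanks should be rare.** Protocol 8.1.3 requires severity and causality for every AE, and 8.1.7 has both the investigator and the sponsor assess causality. This stands and is the main reason the point is minor.
- **The SAP was written to another protocol version.** It cites version 9.0 of 03Nov2022, while the supplied protocol already reports the early stop of Cohort B. This stands too. A reader might infer that the SAP 9 statement is false, but the text of 9.2 in version 9.0 is not available, and the sentence carries an unidentified exception. What can be said is that SAP 9 names neither difference and that the two documents as supplied disagree.
- **Deaths are not hidden.** A reader might infer that a fatal AE could vanish. Outcome is captured for every AE, and all deaths are summarised and listed. The error is confined to the severity-grade table.

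Three further readings are tempting but unsupported:

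- **An imputed related Grade 4 event could suspend Phase 1 accrual.** Suspension is a sponsor action on actual events. Nothing feeds a table convention into it, and SAP 7.7.1 takes DLTs from the CRF record, so the BLRM is untouched.
- **Causality would be blank mainly for pre-dose or procedure events.** No text says so, and Protocol 8.1.3 sends non-serious AEs between main consent and first infusion to medical history.
- **A partial progression date would lengthen PFS.** The documents do not say how such a case is handled, so the direction is unknown.

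**Conclusion.** The inconsistency is real and minor. As supplied, the SAP adds two value imputations that Protocol 9.2 excludes and omits one date imputation that it names. Neither document has a usable rule for partial response-assessment dates. The Grade 4 rule gives a wrong entry for a fatal AE with a blank grade.

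The affected outputs are the Grade 3-or-higher, severity-grade and related AE/SAE tables and, when an assessment date is partial, PFS, DOR and the two confirmation intervals. The size per affected record is 2.4 to 50 percentage points in the AE tables, depending on the group and assuming no other qualifying AE in that subject. For dates it is up to about one month. The overall effect depends on how many fields are blank, which the documents do not report, and it is nil if none are.

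**What to change.** 1. **State one rule.** Either add AE severity and causality to the exceptions in Protocol 9.2, or list the imputation as a deviation in SAP 9. In either case, also show the AE tables without imputation.
2. **SAP 7.8.2:** assign Grade 5 to a blank grade when the AE outcome is fatal, and Grade 4 only otherwise. This is itself an imputation, so the exception or deviation in item 1 must cover it.
3. **SAP 7.3:** add a rule for partial response-assessment dates, for example the imaging date, with any imputed day bounded by the previous assessment and the first dose. Alternatively, remove that item from Protocol 9.2.

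The cost is SAP wording and one additional AE table. The routes that change Protocol 9.2 also need protocol wording. No new data are needed.

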9.3 Statistical Analyses

9.3.1 Characteristics Demographics, Medical History, Prior Medication, and Other Baseline

Demographic characteristics, prior anti-cancer therapies and surgeries, medical history, prior medication, and other baseline data will be listed and summarized using descriptive statistics for numerical data and contingency tables for categorical data. Medical history and prior medication will be listed. Prior anti-cancer therapies will be coded by World Health Organization Anatomical, Therapeutic and Chemical terms and summarized. Prior cancer surgeries will be summarized.

9.3.2 Study Drug

Exposure to AFM24 will be summarized with descriptive statistics for the total number of infusions received. The total amount of time on AFM24 (duration of dosing in weeks) will also be derived and summarized. The number of infusions with interruptions (regardless of reason) will be summarized by dose cohorts and total.

9.3.3 Concomitant Medication

Concomitant medication and significant non-drug therapies after the start of study drug will be listed and summarized by World Health Organization Anatomical, Therapeutic and Chemical term in contingency tables.

9.3.4 Primary Analysis

9.3.4.1 Phase 1 (Dose Escalation)

An adaptive BLRM guided by the EWOC principle will be used in the dose escalation. The use of Bayesian response adaptive models for Phase 1 studies has been advocated by the European Medicines Agency adopted guideline on small populations (EMA, 2006) and by (Rogatko et al., 2007) and is one of the key elements of the FDA's Critical Path Initiative.

A 2-parameter BLRM (Neuenschwander et al., 2008) will be used for dose escalation of the monotherapy. Standardized doses will be used such that 1 of the doses (d^*) equals 1, eg, doses are rescaled as d/d^* . Consequently, α is equal to the odds of the probability of toxicity at d^* . All information currently available about the dose-DLT relationship of AFM24 is summarized in a prior distribution. For this study, this includes preclinical data about the starting dose and predicted MTD of AFM24 within different animal species. This prior distribution is then updated after each cohort of subjects with all the DLT data available in the DDS from the

current study. Once updated, the distribution summarizes the probability that the true rate of DLT for each dose lies in the following categories:

- 0% to <16%: under-dosing;
- ≥16% to <33%: targeted toxicity; and
- ≥33% to 100%: excessive toxicity.

The EWOC principle (Babb et al., 1998; Neuenschwander et al., 2008) mandates that any dose of AFM24 that has more than a 25% chance of being in the excessive toxicity category is not considered for the next dose cohort. A clinical synthesis of the available toxicity information (including AEs that are not DLTs), PK, PD, and efficacy information as well as the recommendations from the Bayesian model, and the SRC will be used to determine the dose regimen for the next cohort at a dose-escalation teleconference. In any case where there is a change in dose schedule, a new model will be defined using a Meta-Analytic-Predictive prior, based on the observed data.

The frequency of DLTs will be tabulated by dose for subjects in the dose escalation phase (Phase 1) (especially for Cycle 1 and subjects in the DDS as the primary endpoint tabulation) and information about all DLTs will be listed by dose.

Bayesian Logistic Regression Model for MTD/RP2D Determination

The objective of the design is to determine the MTD defined as the highest dose with less than 25% risk of the true DLT rate being above 33%. The escalation Phase 1 dose-finding will be guided by a Bayesian 2-parameter logistic regression model with overdose control. These designs have been shown to be superior regarding the precision of MTD determination compared with 3+3 designs.

The model is formulated as follows:

$$\text{logit}(p(d)) = \log(\alpha) + \beta * \log(d/d^*),$$

where $\text{logit}(p) = \log(p/(1-p))$. $p(d)$ represents the probability of having a DLT in the first cycle at dose d , $d^* = 180$ mg is the reference dose, allowing for the interpretation of α as the odds of a DLT at dose d^* , and $\theta = (\log(\alpha), \log(\beta))$ with $\alpha, \beta > 0$ is the parameter vector of the model.

Since a Bayesian approach is applied, a prior distribution $\pi(\theta)$ for the unknown parameter vector θ needs to be specified. This prior distribution will be specified as a multivariate normal distribution, ie,

$$\pi(\theta) = \text{MVN}(\mu, \Sigma)$$

the multivariate normal distribution with mean vector μ and covariance matrix Σ , with

$$\Sigma_i = \begin{pmatrix} \sigma_{i,11}^2 & \sigma_{i,11}\sigma_{i,22}\rho_i \\ \sigma_{i,11}\sigma_{i,22}\rho_i & \sigma_{i,22}^2 \end{pmatrix}$$

Prior derivation

For the current study, data from the non-clinical animal studies were available. Therefore, the observed toxicity data from a study in animals is used to derive the prior.

Prior from nonclinical data:

The starting dose of AFM24 will be 14.0 mg ($200 \mu\text{g}/\text{kg} \times 70 \text{ kg}$ body weight), which is presumed to be at the lower end of the pharmacologically active dose range. No critical toxicities were observed in the cynomolgus toxicity studies up to the maximum applied AFM24 dose level of 75 mg/kg and furthermore, the bispecific NK engagers (in contrast to bispecific T cell engagers) tested so far by Affimed in nonclinical and clinical studies, were all well tolerated up to high dose levels. It is therefore highly unlikely that a severe toxicity defined as DLT in this study would occur at this starting dose, leading to the prior assumption that the median DLT rate at 14 mg is 0.1%. On the other hand, assuming dose-proportionality in humans using a cautious approach, the median DLT rate at the highest planned dose = 1000 mg was therefore assumed 25%.

Table 8: Summary of Prior Distribution

Mean vector	STD vector	Correlation
-1.983 -0.217	2.000, 1.000	0

STD = standard deviation.

A summary of the prior probabilities of DLT at different doses, as well as the corresponding probability of under-, targeted, and overdosing, are shown in [Table 9](#). Graphically, the prior medians with accompanying 95% credible intervals are shown in [Figure 3](#). As can be seen from both [Table 9](#) and [Figure 3](#), the prior medians of the DLT probabilities are in line with the prior median derived from the non-clinical studies.

[figure not shown]
Table 9: Prior Probabilities of DLT at Selected Doses

Dose	Probability of true DLT rate in			Mean	STD	Quantiles		
	[0–0.16)	[0.16–0.33)	[0.33–1]			2.5%	50%	97.5%
7 ^a mg	0.888	0.058	0.054	0.061	0.138	0.000	0.006	0.533
14 mg	0.859	0.072	0.069	0.075	0.153	0.000	0.011	0.597
40 mg	0.795	0.097	0.108	0.108	0.182	0.000	0.026	0.699
120 mg	0.655	0.148	0.196	0.178	0.227	0.001	0.074	0.821
360 mg	0.538	0.175	0.288	0.244	0.261	0.003	0.134	0.892
1000 mg	0.415	0.166	0.419	0.342	0.311	0.005	0.236	0.974

DLT = dose-limiting toxicity; STD = standard deviation.

Doses printed in bold type meet the overdose criterion, $P(\text{overdose}) < 0.25$.

^a Dose level -1 represents a dose that may be evaluated if dose level 1 is poorly tolerated. No dose de-escalation below this level is planned for this study. If dose-level -1 is poorly tolerated the study will be terminated.

Figure 3: Prior Medians and 95% Credible Intervals

CrL = credible interval; MTD = maximum tolerated dose; RP2D = recommended Phase 2 dose.

For MTD and/or RP2D definition, please refer to Section 3.4.3.

Statistical model assessment

The single agent model was assessed using 2 different metrics:

Hypothetical data scenarios: for various potential data constellations as they could occur in the actual study, the maximal next doses as allowed by the model and by the 200% escalation limit are investigated. Data scenarios thus provide a way to assess the “on-study” behavior of the model.

2. Simulated operating characteristics: these illustrate for different assumed true dose-toxicity relationships, how often a correct dose would be declared as MTD by the model. They are a way to assess the “long-run” behavior of the model.

In summary, the model showed very good behavior as assessed by these metrics. More details can be found in Appendix E (Section 14.5).

